10.1 Ethical Conduct of the Study

The study will be conducted in accordance with the protocol and the requirements according to the concerned laws. The project will be submitted to the supervision parties for censorship. The study will be initiated only with the approval of the IRB & HEC. All the data and information collected from the study will be presented to the supervision parties, especially the information related to AE & SAE. Alteration of the project plan will not be made without the consideration and authorization of the supervision parties. A full report will be provided after the closure of the study.

Shanghai Jiao Tong University, WF220441504

Collaborators: Key Laboratory of Systems Biomedicine,
Shanghai Jiao Tong University

Version 2.0

Version Date: April 12, 2020

Brief Summary:

The purpose of this study is to evaluate the safety, tolerability and efficacy of a single dose of CRISPR/Cas9 mRNA Instantaneous Gene Editing Therapy administered via corneal injection in participants with refractory herpetic viral keratitis.

Condition or disease	Intervention/treatment
Herpes Simplex Virus Infection	Drug: HELP (BD111) Adult single group Dose
Refractory Viral Keratitis	(Administered by corneal injection surgery. Dosage form: injection solution. Dose: 200µL. Frequency of administration: one time injection.)

Description:

This is a single-arm, single dose study of mRNA-carrying HELP (HSV-1-erasing lentiviral particles) in adult (ages 18 to 70) participants with refractory herpetic viral keratitis. 3-6 participants will be enrolled and receive HELP injection during the usual procedure of corneal transplantation. HELP is a novel gene editing formulation designed to clear Herpes simplex virus type I (HSV-1) that results in herpetic stromal keratitis in both acute and recurrent infection models which is the leading factor for infectious blindness. The main outcomes of this study include HSV-1 testing outcome, graft survival, visual acuity and adverse effects of the participants.

Outcomes Measures:

1. Primary Outcome Measure

HSV-1 testing results of the intervention eye. Tear swab of 1 week, 1 month, 2 months, 3 months, 6 months and 12 months post-operation will be collected and quantified for HSV-1 genome by real-time polymerase chain reaction (RT-PCR). The virus testing outcome was indicated as positive (+) or negative (-) by Ct values. Ct value of above 40 will be considered negative, 36-40 be considered weakly positive, and below 35 will be considered a strong positive.

2. Secondary Outcome Measure

- ⑩ Patient graft survival. The corneal grafts of participants will be monitored under a complete ophthalmic examination, including slit-lamp examination and anterior segment optical coherence tomography (OCT), at every follow up visit.
- ⑩ Best-corrected visual acuity. Changes of visual acuity of participants along the clinical trial.
- ⑩ Adverse effects, including possible alteration of ocular structure and function, Cas9-specific immunoreaction or off-target editing of CRISPR in the bloodstream. Postoperative B-scan ultrasonography, time-domain OCT, spectral-domain OCT, and electroretinography (ERG) will be used to evaluate ocular status. ELISA and Whole-genome sequencing (WGS) will be conducted on the blood samples collected at 3-month and 6-month visit, respectively.

Table of Contents

1. Introduction	30
1.1 Study Objects.....	30
1.2 Backgrounds of HELP.....	30
2. Eligibility Criteria	30
2.1 Inclusion Criteria.....	30
2.2 Exclusion Criteria.....	31
3. Study Implementation	32
3.1 Study Design.....	32
3.2 Preparation of HELP Formulation.....	33
3.3 Corneal Transplant and HELP Administration.....	34
3.4 Post-operation Management.....	35
4. CRISPR/Cas9 Therapy Interruption	36
5. Quality Control	36
5.1 Quality Control and Quality Assurance.....	36
5.2 Monitoring.....	36
6. Data Collection and Evaluation	37
7. Statistical Considerations	38
8. Adverse Event Reporting	38
8.1 Adverse Event.....	38
8.2 Serious Adverse Event.....	38
8.3 Recording and Reporting.....	39
9. Record Form & Retention	40
10. Ethics	40

10.1	Ethical Conduct of the Study.....	40
10.2	Patient Information and Consent.....	40
11.	Reference.....	42

1. Introduction

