Identifier: NCT04560790

Official Title:

**CRISPR/Cas9 mRNA Instantaneous Gene Editing Therapy
Assisted Corneal Transplantation in the Treatment of
Refractory Viral Keratitis**

Date: April 12, 2020

Protocol

Unique Protocol ID: JYMS-CXL#02

This trial protocol has been provided by the authors to give readers additional information about their work.

DESCRIPTION

This supplement contains the following items:

1. Original protocol, final protocol, summary of changes.
2. Original and final statistical analysis plan.

Table of Contents

ORIGINAL STUDY PROTOCOL	5
CURRENT STUDY PROTOCOL.....	24
SUMMARY OF PROTOCOL CHANGES	43
ORIGINAL AND CURRENT STATISTICAL ANALYSIS PLAN.....	45

Original Study Protocol

Protocol Approval ID: 2020023-2-v1

**Safety and Efficacy of CRISPR/Cas9 mRNA Instantaneous Gene
Editing Therapy to Treat Refractory Viral Keratitis**

Investigator: [name]., Ph.D, M.PA.
Deputy Chief Physician
Department of Ophthalmology and Visual Science

Research Institute: Eye, and ENT Hospital,
Shanghai Medical College, Fudan University, Shanghai, China

Founding: National Natural Science Foundation of China,
81970766, 8217040684 and 31971364
the Program for Professor of Special Appointment
(Eastern Scholar) at Shanghai Institutions of Higher Learning,
TP2019046
The Shanghai Innovation Development Program,
2020-RGZN-02033
the Shanghai Key Clinical Research Program,
SHDC2020CR3052B
Startup funding from Shanghai Center for Systems Biomedicine
Shanghai Jiao Tong University, WF220441504

Collaborators: Key Laboratory of Systems Biomedicine,
Shanghai Jiao Tong University

Version 1.0

Version Date: December 28, 2019

Brief Summary:

The purpose of this study is to evaluate the safety, tolerability and efficacy of a single dose of CRISPR/Cas9 mRNA Instantaneous Gene Editing Therapy administered via corneal injection in participants with refractory herpetic viral keratitis.

Condition or disease	Intervention/treatment
Herpes Simplex Virus Infection	Drug: HELP (BD111) Adult single group Dose
Refractory Viral Keratitis	(Administered by corneal injection surgery. Dosage form: injection solution. Dose: 250µL. Frequency of administration: one time injection.)

Description:

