3.2 Preparation of HELP Formulation

HELP (BD111) was produced following Good Manufacturing Practice (GMP) guidelines. Briefly, 293T cells were seeded in 10-tray stacks cell factory (Thermo Fisher Scientific) and transfected with 6 packaging plasmids using PEI. Cell culture medium was refreshed 6 h post-transfection. Supernatants were harvested 48 h later and pooled before filtration through 0.45 µm. The downstream purification process included a benzonase treatment overnight at 4°C, followed by ultrafiltration and purification using ion-exchange chromatography. The resulting BD111 was dissolved in PBS, passed through 0.22-µm filters, and stored at -80°C.

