3.3.4 HELP Administration

The HELP formulation stored in -80°C will be transferred in 4 °C from the lab to the surgery room 30 min earlier. Then it will be recovered to the room temperature 10 min before its usage, where in total of 0.25 ml formulation is drawn into a 27g ophthalmic syringe for the later injection. Penetrating keratoplasty will be performed following the routine procedures described above. After sewing up the donor cornea, the HELP formulation in the syringe is injected in evenly divided 6-8 locations of the recipient graft bed. The indication for its successful entrance into the stroma will be the visible edema and whitening of the corneal bed in the injection sites, which should cover the entire recipient bed area in the end.

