10.2 Patient Information and Consent

All participants and/or their legal representatives will be fully informed of the objectives and details of this study. All possible outcomes and risks will be acknowledged. A consent of written form will be obtained from each patient or their representatives. The consent process will be witnessed by an

impartial supervisor. A copy of the consent will be provided if requested by the participants. The consent documents will be stored by the investigators along with other data collected during the study for a period required by the protocol. All the personal information and data from the patients will only be available to the investigators and supervision parties to guarantee privacy. The data will not be used for purposes other than this study.

11 Reference

Summary of Protocol Changes

Section of Current protocol	Rationale	Current Version
Basic Information	Adjust the number of participants enrolled	3-6 participants will be enrolled and receive HELP injection during the usual procedure of corneal transplantation.
Outcomes Measures	Adjust the contents and priorities of outcomes	Primary outcome: HSV-1 testing outcome of the intervention eye; Secondary outcome: patient graft survival; best-corrected visual acuity; adverse effects

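### The current protocol gives two volumes for the single HELP dose, 200 µL in the intervention table and 0.25 ml in section 3.3.4, a 25% difference

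*Combined protocol and SAP*

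**What the plan says.** The current protocol (Version 2.0) states the amount of HELP in two places.

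- Brief Summary, intervention table: "Dosage form: injection solution. Dose: 200µL. Frequency of administration: one time injection".
- Section 3.3.4, HELP Administration: "in total of 0.25 ml formulation is drawn into a 27g ophthalmic syringe for the later injection". After the donor cornea is sutured, "the HELP formulation in the syringe is injected in evenly divided 6-8 locations of the recipient graft bed".

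Section 3.3.4 mentions no dead volume, overfill or discarded remainder. It judges success by visible swelling and whitening of the bed, not by a delivered volume.

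Version 1.0 was consistent. Its intervention table read "Dosage form: injection solution. Dose: 250µL. Frequency of administration: one time injection", and its section 3.3.4 had the same 0.25 ml wording that Version 2.0 still carries.

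The Basic Information row of the Summary of Protocol Changes gives its reason as "Adjust the number of participants enrolled". The other rows cover outcomes and inclusion criteria, and none mentions dose. The statistical analysis plan refers to a single dose without giving a volume. Section 3.2 describes the product only this far: "The resulting BD111 was dissolved in PBS, passed through 0.22-µm filters, and stored at -80°C". No titre, particle count or concentration appears.

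**The concern.** The trial tests one dose of a gene-editing product in one arm of 3-6 people. HSV-1 results, graft survival, visual acuity, immune response and off-target findings will all be attributed to that dose, and there is no second dose group to anchor it. Because volume is the only dose measure given, two different volumes leave the exposure under test undefined.

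The main risk is misreporting. Surgeons will probably work from section 3.3.4, the only step-by-step instruction, while a report or registry entry would naturally take its figure from the intervention table. The published dose would then be wrong, and anyone choosing a dose for later work would start from the wrong number. It is also possible that participants receive different volumes. Neither section 3.3.4 nor section 6 asks for the injected volume to be recorded, so the data as described would not show it.

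There is a governance side too. Section 10.1 requires authorisation before the plan is altered. With two volumes in the text and no dose entry in the change summary, a reader cannot tell which dose was authorised.

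**Working it through.** **Inputs**

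| Source | Intervention table | Section 3.3.4 | In µL |
|---|---|---|---|
| Version 1.0 | 250 µL | 0.25 ml | 250 and 250 |
| Version 2.0 (current) | 200 µL | 0.25 ml | 200 and 250 |

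**Step 1. Convert units.** 0.25 ml × 1000 = 250 µL. This reproduces the Version 1.0 table figure, so that version agrees with itself. It does not reproduce the Version 2.0 table figure of 200 µL.

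**Step 2. Size of the difference in Version 2.0.**

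- Absolute: 250 − 200 = 50 µL.
- Relative to the table: 50/200 = 0.25, so the procedure volume is 25% higher (250/200 = 1.25).
- Relative to the procedure: 50/250 = 0.20, so the table is 20% lower (200/250 = 0.80).

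**Step 3. Volume per injection site.** Section 3.3.4 divides the total evenly over 6 to 8 sites.

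| Total | 6 sites | 8 sites |
|---|---|---|
| 200 µL | 200/6 = 33.3 µL | 200/8 = 25.0 µL |
| 250 µL | 250/6 = 41.7 µL | 250/8 = 31.25 µL |

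The two ranges overlap, so the volume placed at a single site would not reveal which total was used.

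**Step 4. Look for anything that reconciles the figures.** For both to be right, 50 µL of each 250 µL drawn (20%) would have to stay in the syringe or be discarded. Section 3.3.4 says nothing of the kind. The change summary is silent on dose. With no concentration given, the two volumes cannot be compared as particle counts either.

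**The case against.** The strongest defence is that 0.25 ml is a draw-up volume with overfill and 200 µL is the delivered dose. Section 3.3.4 says what is drawn. It never gives a delivered volume or says explicitly that the syringe is emptied, and its visual endpoint could be reached before all of it is used. On that reading the 25% is a maximum that applies only if the whole draw is injected. The reading is possible but has no support in the text. No remainder is mentioned, what is injected is described as the formulation in the syringe, and Version 1.0 paired the same procedure wording with a stated dose of 250 µL, which treats the drawn volume as the dose.

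Three further objections are fair as limits on the point:

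- The difference is one of volume. Without a titre, reconciling the two figures does not by itself define the biological dose. This makes volume more important as the only stated measure, but 25% should not be read as a bound on uncertainty in particles delivered.
- Differing volumes between participants are a possibility only. Section 6 requires the same procedures for every patient unless noted, so a uniformly misreported dose is the likelier harm. Likewise, Version 2.0 plans no further dose level, so the effect on a later dose choice lies outside this trial.
- No sample-size, power or significance calculation depends on the dose, and the primary endpoint is only summarised descriptively. The error does not change how any endpoint is analysed. It changes the exposure that the results describe.

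None of this removes the contradiction between two statements in the current text.

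**Conclusion.** The point holds, and the text is wrong as written. Version 2.0 states a single dose of 200 µL in one place and instructs 250 µL in another, a gap of 50 µL: 25% on the lower figure, 20% on the higher. Taken as written, the procedure gives every participant 25% more than the stated dose. This assumes that the syringe contents are injected in full, as the plain reading of section 3.3.4 suggests.

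The likely cause is an incomplete edit between versions, since only the table changed, but that is an inference. The documents do not show which volume is intended, and they give no basis for estimating the clinical effect of 50 µL. The correction must still be made, because this figure is the only definition of dose in a first-line description of a single-dose gene-editing trial.

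**What to change.** State one volume in both the intervention table and section 3.3.4. If 0.25 ml is meant as the drawn volume and 200 µL as the injected dose, label them that way in both places and say what happens to the remaining 50 µL. The sponsor must decide which figure is correct. Enter any change of dose in the Summary of Protocol Changes so that the authorised figure is traceable.

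Record the volume actually injected for each participant and report the safety and HSV-1 results against it.

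The cost is a wording correction and one case-report-form field, with no extra patients or procedures.

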1.1 Study Objectives

The primary objective of this study is to evaluate the HSV-1 erasing efficiency of HELP with the assistance of corneal transplantation for the treatment of refractory HSK patients. The secondary objective is to determine the safety of CRISPR/Cas9 mRNA Instantaneous Gene Editing Therapy in the form of intracorneal injected HELP. In addition, potential long-term off-target effect of HELP injection should also be determined during the 360 days of follow-ups.

1.2 Backgrounds

HELP, mRNA-carrying lentiviral particle that delivers SpCas9 mRNA and a guide RNA-expressing cassette targeting HSV-1 genome (designated HSV-1-erasing lentiviral particle, termed HELP). The viral genome encodes two guide RNAs simultaneously targeting HSV-1 UL8 and UL29 gene, respectively, and is co-packaged with SpCas9 mRNA in the lentiviral particle. The gRNA expression cassette is reverse transcribed in the integration-defective lentiviral vector and maintained as circular episomal DNA in the nucleus. Lentiviral delivery has been reported increasingly in gene therapy and is tolerated in the clinical trials as reported in other studies.¹⁻⁵ In the preclinical study, HELP efficiently blocks HSV-1 replication and the occurrence of herpetic stromal keratitis (HSK) in different corneal infection models without finding notable adverse effects.⁶

2. Eligibility Criteria

2.1 Inclusion Criteria

- ⑩ Age between 18 to 70 years old;
- ⑩ No systemic immune eye disease;
- ⑩ Good eyelid structure and blink function;
- ⑩ Exists the potential of visual recovery by evaluation of ocular structure and function;

- ⑩ Patients with refractory keratitis who are repeatedly infected with HSV-1 virus (more than three times per year) and resistant to topical or systemic anti-viral agents, with no response to regular immunosuppressive agents;
- ⑩ Patients who are obviously suffering from relapse HSV infections with corneal perforation, requiring corneal transplantation;
- ⑩ No history of corneal trauma;
- ⑩ Subjects or their legal guardians voluntarily participate in this study, sign informed consent, good compliance and cooperation with follow-up visits.

2.2 Exclusion Criteria

- ⑩ Lacrimal coating and blink function loss;
- ⑩ Schirmer's test result is less than 2mm for severe dry eye disease;
- ⑩ Pregnant and lactating women (pregnancy defined in this study as positive urine pregnancy test);
- ⑩ Currently is involved in clinical trials of other drugs or medical devices;
- ⑩ Active eye infection (including but not limited to: blepharitis, infectious conjunctivitis, keratitis, scleritis, endophthalmitis) in target eye or contralateral eye within 30 days prior to enrollment;
- ⑩ Ocular surface malignant tumor;
- ⑩ A history of allergic reaction or allergy to sodium luciferin, allergy to protein products used for treatment or diagnosis, allergy to ≥ 2 drugs or non-drug factors, or current allergic disease;
- ⑩ current in an infectious disease requiring oral, intramuscular or intravenous administration;
- ⑩ Patients with systemic immune diseases;
- ⑩ Any uncontrolled clinical problems (such as severe mental, neurological, cardiovascular, respiratory and other systemic diseases and malignant neoplasms);
- ⑩ Not effective contraception;
- ⑩ In uncontrolled hypertension, systolic is no less than 160 mmHg, diastolic is no less than 100 mmHg;
- ⑩ In uncontrolled diabetes, fasting glucose is no less than 10.0umol/L;

- ⑩ Renal insufficiency, serum creatinine is more than 133 μ mol/L;
- ⑩ Arrhythmia, myocardial ischemia, myocardial infarction (diagnosed by electrocardiogram);
- ⑩ Liver dysfunction, al ANINE aminotransferase and aspartate aminotransferase levels are higher than 80 IU/L;
- ⑩ Platelet level is below 100,000 / μ L or above 450,000 / μ L;
- ⑩ Hemoglobin level is below 10.0g/dL (male) or 9.0g/dL (female);
- ⑩ No anticoagulant was used, prothrombin time is higher than 16s, and thrombin time of activated part is higher than 50s;
- ⑩ HIV infection (HIV-positive);
- ⑩ Subjects lack compliance with the study or the ability to sign informed consent;
- ⑩ There are currently signs of systemic infection, including fever and ongoing antibiotic treatment (in this study, systemic infection was defined as deviation from normal values of white blood cells, lymphocytes, and neutrophils on routine blood tests);
- ⑩ Administration of Glucocorticoids and other systemic immunosuppressive drugs;
- ⑩ The investigator judges other conditions unsuitable for the trial

3. Study Implementation

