3.1 Study Design

The enrollment of participants initiates relevant processes immediately. After the completion of preoperative examinations, participants with corneal perforation will be arranged for transplantation as soon as possible. During the usual procedure of the surgery, CRISPR/Cas9 mRNA formulation in the form of HELP will be administrated for the treatment of refractory HSK. The hospital observations of participants will persist for 7 days. The postoperative recovery condition, HSV-1 testing outcome, adverse effects of the participants will be examined at every follow-up time. After their hospital discharge on 7th day, follow-up will be conducted on 1 month, 2 months, 3 months, 6 months and 12 months after the surgery. The basic information is shown in the Table 1. below.

Table 1. Basic Information of Our Clinical Study

Item	Content
Study Type	Interventional (Clinical Trial)
Estimated Enrollment	3-6 participants
Allocation	N/A
Intervention Model	Single Group Assignment
Intervention Model Description	Single group target value: Since there is no similar products approved on the market or similar comparative treatment methods, the single group target value method is adopted
Masking	None (Open Label)
Primary Purpose	Treatment
Actual Study Start Date	November 4, 2020
Estimated Primary Completion Date	November 2021
Estimated Study Completion Date	May 2022

In this study, each participant diagnosed with terminal refractory HSK will undergo HELP injection during the normal procedure of penetrating keratoplasty (PK). Before the surgery, they will receive conventional topical or systemic antiviral treatment. During the operation, single dose CRISPR/Cas9 mRNA formulation in the form of HELP will be injected into the recipient graft bed. Then the participants will no longer receive any forms of antiviral treatment unless occurs an uncontrollable virus recurrence, when the conventional antiviral therapy continues. At follow-up visits, participants will undergo a series of examinations, including best-corrected visual acuity, intraocular pressure, photograph of anterior segment, postoperative B-scan ultrasonography, time-domain optical coherence tomography (OCT), spectral-domain OCT, electroretinography (ERG), ELISA of blood samples, deep sequencing of corneal epithelial cells, HSV-1 testing and potential adverse events.

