This is an open-label, single-arm clinical study. The investigators conducted this research to evaluate the safety and efficacy of HSV-1-targeting CRISPR formulation HELP for in vivo treatment of refractory HSK patients. In this study, participants will receive a single dose of HELP formulation by intrastromal injection during the penetrating keratoplasty for acute corneal perforation. At each follow-up point, a series of safety and effectiveness evaluations will be performed.

The primary endpoint, HSV-1 in tear swabs will be evaluated at various test points according to the data collection plan, as summarized by simple descriptive summary. For safety evaluations, clinical examinations (slit-lamp examination, measurement of best-corrected visual acuity, intraocular pressure, B-scan ultrasonography, the time-domain OCT, the spectral-domain OCT, and the ERG) will be presented as simple descriptive statistics in the form of pictures, line charts or summarized tables. Deep sequencing of the corneal epithelial cells (acquired by corneal wipes) will also be reported as descriptively summarized tables. Blood ELISA will be reported graphically with the aid of the Student's test. Other laboratory and imaging correlative studies will also be reported descriptively and graphically.

8. Adverse Event Reporting

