2.1	Adjust the inclusion criteria	Patients with refractory keratitis caused by herpes virus type I who has acute corneal perforation or had at least one time failed corneal transplant due to the virus relapse.

Original and Current Statistical Analysis Plan

Statistical Analysis Plan

This is an open-label, single-arm, non-randomized interventional trial. The investigators conducted this research to evaluate the safety and efficacy of HSV-1-targeting CRISPR formulation HELP (BD111) for in vivo treatment of refractory HSK patients. In this study, participants will receive a single dose of HELP formulation by intrastromal injection during the penetrating keratoplasty for acute corneal perforation. At each follow-up point, a series of safety and effectiveness evaluations will be performed.

The primary endpoint, HSV-1 in tear swabs will be evaluated at various test points according to the data collection plan, as summarized by simple descriptive summary. For safety evaluations, clinical examinations (slit-lamp examination, measurement of best-corrected visual acuity, intraocular pressure, B-scan ultrasonography, the time-domain OCT, the spectral-domain OCT, and the ERG) will be presented as simple descriptive statistics in the form of pictures, line charts or summarized tables. Deep sequencing of the corneal epithelial cells (acquired by corneal wipes) will also be reported as descriptively summarized tables. Blood ELISA will be reported graphically with the aid of the Student's test. Other laboratory and imaging correlative studies will also be reported descriptively and graphically. Data were analysed using GraphPad Prism 8 and presented as mean \pm SEM in all experiments (n=3). Unpaired two-tailed Student's t-tests were performed to determine the P values (95% confidence interval). n.s., non-significant.

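### Section 2.2 excludes active keratitis in the study eye with no exemption for the HSV-1 keratitis being treated, so the perforated-relapse patients in 2.1 are ineligible as written; the printed glucose limit separates no one

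*Combined protocol and SAP*

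**What the plan says.** All references are to the current protocol, version 2.0, unless stated.

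- **Section 2.2, infection item.** Active eye infection is an exclusion. The examples include "keratitis, scleritis, endophthalmitis) in target eye or contralateral eye within 30 days prior to enrollment". There is no carve-out for HSV-1.
- **Section 2.1, two HSV items.** One begins "Patients with refractory keratitis who are repeatedly infected with HSV-1 virus (more than three times per year" and goes on to require resistance to antiviral agents. The other reads "Patients who are obviously suffering from relapse HSV infections with corneal perforation, requiring corneal transplantation". The text does not say whether a patient must meet both or only one.
- **Section 3.1.** After the preoperative examinations, "participants with corneal perforation will be arranged for transplantation as soon as possible".
- **Section 7.** It states without qualification that "participants will receive a single dose of HELP formulation by intrastromal injection during the penetrating keratoplasty for acute corneal perforation". The SAP likewise has the product given "by intrastromal injection during the penetrating keratoplasty for acute corneal perforation".
- **Section 2.2, glucose item.** "In uncontrolled diabetes, fasting glucose is no less than 10.0umol/L". Version 1.0 prints the same figure and unit.
- **Section 2.2, infectious-disease item.** A patient is excluded if "current in an infectious disease requiring oral, intramuscular or intravenous administration". Section 3.3.1 lists oral acyclovir among the preoperative medications, up to the eve of surgery.

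**The concern.** The disease that qualifies a patient under 2.1 is named as a reason for refusal under 2.2. A screener who applies 2.2 to the letter must turn away the perforated-relapse patients described in section 7 and the SAP. Each one enrolled is then either a protocol deviation or an admission that rests on no written rule.

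With 3-6 participants, one disputed eligibility decision concerns between 1/6 = 17% and 1/3 = 33% of the data. The rule also decides whether participants may enter with active HSV-1 infection. That matters for reading the primary outcome, which is HSV-1 in postoperative tear swabs in a single arm with no comparator.

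The glucose item is a safety exclusion with a numeric cut-off. If the number cannot tell patients apart, the cut-off does nothing.

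**Working it through.** **1. Infection conflict: one patient tested against both sections**

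Take a patient who meets the perforation item of 2.1 and check each element of the 2.2 item.

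- *Condition:* active infection, with keratitis named. A current HSV relapse that has perforated the cornea is taken here as active infectious keratitis. This is an assumption, but it is the natural reading. Met.
- *Eye:* target or fellow eye. The perforated eye is the one to be grafted and injected, so it is the target eye. Met.
- *Window:* 30 days before enrolment. The relapse is current at enrolment, so it falls inside the window. Met.
- *Exemption:* none in 2.2 and none found elsewhere.

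The same patient is therefore listed in 2.1 and barred by 2.2.

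**2. Does anything else in the protocol resolve it?**

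- *Timing.* Section 6 places screening 3-14 days before treatment. The longest interval, 14 days, is shorter than the 30-day look-back, and section 3.1 asks for prompt surgery. Neither provides an infection-free period.
- *Investigator judgement.* The last item of 2.2 lets the investigator add exclusions. It does not allow one to be waived.
- *Changes to the plan.* Section 10.1 allows changes with authorisation of the supervising bodies. It describes no case-by-case waiver.
- *Revision history.* The infection exclusion, keratitis included, is also in version 1.0. Section 2.1 was revised for version 2.0, but this item gained no exemption.

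**3. How many participants are affected?**

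Let n be the number enrolled (3 to 6) and k the number admitted through the perforation item.

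- *Both HSV items required (AND):* k = n, so 3 of 3 up to 6 of 6.
- *Either item sufficient (OR):* k lies between 0 and n, so 0 to 6. The other route need not be empty. More than three infections a year means at least four, an average spacing of at most 365 / 4 ≈ 91 days. A clear interval of over 30 days is therefore possible.

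The documents do not give k. Section 7 and the SAP describe every participant as having surgery for acute perforation, which points to the upper end.

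**4. Glucose limit**

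Printed limit: 10.0 µmol/L / 1000 = 0.010 mmol/L.

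The documents give no distribution of fasting glucose. Assume 2-10 mmol/L:

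- 2 / 0.010 = 200
- 10 / 0.010 = 1000

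Values in that range are 200 to 1000 times the limit. Extending the assumed range to 30 mmol/L gives 30 / 0.010 = 3000. No assumed value falls below the limit, so all of them count as being at or above it. The consequence depends on how the item is read:

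- *As a stand-alone limit:* everyone is excluded.
- *As a condition applied within uncontrolled diabetes:* everyone in that group meets it, so the number adds nothing.

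Under neither reading does the number separate patients.

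**5. Oral treatment**

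The infectious-disease item in 2.2 turns on a need for oral, intramuscular or intravenous treatment. Section 3.3.1 lists an oral antiviral for participants before surgery. The item does not say whether treatment of the study disease counts. This is an ambiguity, not a demonstrated contradiction.

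**The case against.** The strongest reply is that the protocol should be read as a whole. Section 2.1 names HSV relapse with perforation as a ground for enrolment, and section 3.1 describes every participant as having terminal refractory HSK. A general list of infections was probably meant to catch infections other than the study disease. On that view only an exempting phrase is missing. The intent is likely, but the text does not state it, and the list names keratitis. Site staff and monitors apply the written rule.

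Second, the size is not fixed: the upper figure needs the AND reading, and 0 to 6 is the whole range. This stands, and it is itself a result of 2.1 not saying how its items combine.

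Third, the glucose line may be only a unit slip. It opens with a reference to uncontrolled diabetes, and 2.2 separately excludes uncontrolled clinical problems in general, so some protection survives. That also stands. The cut-off itself still does not work, and because it is printed identically in both protocol versions, a PDF-reading error is unlikely. Nothing in the documents shows whether the number or only the unit is wrong.

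Fourth, the infectious-disease item can be read as covering non-ocular disease, since eye infection has its own item. That is reasonable, and this point is given less weight for that reason.

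Finally, the SAP refers to n=3 and reports its methods in the past tense, so enrolment may be over. If so, an account of how 2.2 was applied is worth more than an amendment.

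**Conclusion.** The concern holds, on two grounds.

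- **Infection exclusion.** Sections 2.1 and 2.2 conflict for every patient in a current HSV relapse with perforation. This covers all 3-6 planned participants if both HSV items are required, and 0 to 6 if either suffices. It rests on treating such a relapse as active keratitis and on applying the text as written.
- **Glucose limit.** As printed, it equals 0.010 mmol/L and separates no patients under either reading. The conversion needs no assumption. The statement that every patient lies above it uses an assumed fasting range starting at 2 mmol/L, 200 times the limit.

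The oral-treatment item is a lesser ambiguity and does not carry the conclusion. The conflict and the glucose limit should be corrected before the eligibility criteria are relied on.

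**What to change.** 1. Reconcile 2.1, 2.2 and 3.3.1. Section 2.2 should say explicitly whether HSV-1 keratitis in the study eye, and antiviral treatment for it, are exempt from the eye-infection and infectious-disease items. Which way to decide is for the sponsor.
2. State in 2.1 whether both HSV items are required or either one suffices.
3. Verify the fasting-glucose value and unit against the source, correct whatever is wrong, and say whether the limit stands alone or applies only within uncontrolled diabetes.
4. Log each participant enrolled under the present wording, recording which HSV item admitted them and how the two infection exclusions were applied. If enrolment has closed, report this with the results.

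The cost is an amendment to the eligibility wording and a short log. It needs no extra procedures or patients.
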